We will include all patients who meet the inclusion criteria. We do not exclude patients based on race, color, national origin, sex, sexual orientation, or religion. We will not enroll vulnerable patient populations in this study.

5. Subject Enrollment

Patients will be prescreened through retrospective manual chart review.

Patients will be contacted in person at one of the MGB hospitals (MGH main campus, MGH Waltham, MGH Danvers, BWH main campus, BWH Faulkner, and BWH Foxborough). Patients who meet the inclusion criteria will get a summary of the study by an orthopedic surgeon or a study staff member to see if they are interested. If patients are interested, they will receive the study fact sheet, and the surgeon or study staff member will explain the study in more detail and answer any questions the patient may have. Subjects will be asked to complete the questionnaire either in person or over email or telephone before surgery. Subjects who opt to not complete the questionnaire in person will be contacted using the email or telephone script approved in this study. Subjects who do not complete the pre-op questionnaire before surgery will be withdrawn. Subjects can opt to receive an encrypted or unencrypted email. Subjects who indicate verbally in the outpatient clinic that they do not wish to participate will not be included in the study.

Depending on the treating surgeon, patients will either be treated with an open trigger finger release or an ultrasound-guided trigger finger release.

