6. STUDY PROCEDURES

Study visits

Visits	Procedures
Visit 1 – before surgery	
- Obtain informed consent- ADL questionnaire (see next section)- Visual analog scale for pain (VAS): pain on a scale of 1 to 10 
The measurements are part of standard care and performed by caregivers
 
- Perform the following measurements: range of motion of the PIP joint of the affected finger (including noting any flexion contracture), distance fingertip to distal palmar crease (DPC), and grip strength using Jamar 2 setting.
Visit/Telephone call 2 (2-4 days after surgery)	
- Take the following questionnaire:
1. Are you able to return to activities of daily living, and what activities do you still have trouble doing? You can list the activities you are having trouble with.2. VAS3. How many oxycodone or other narcotic medications are you taking post-op4. Are you able to return to work?

	
5. Are you satisfied with the procedure, and would you choose to have it again for a similar problem?
 
- Take the ADL questionnaire (see next section)- If in person (part of standard care, only collected by study staff, measurements performed by caregivers): Perform the following measurements: range of motion of the PIP joint of the affected finger (including noting any flexion contracture), distance fingertip to distal palmar crease (DPC), and grip strength using Jamar 2 setting.
Visit/Telephone call 3 (6-8 days after surgery)	
- Take the following questionnaire:
1. Are you able to return to activities of daily living, and what activities do you still have trouble doing? You can list the activities you are having trouble with.2. VAS3. How many oxycodone or other narcotic medications are you taking post-op4. Are you able to return to work?5. Are you satisfied with the procedure, and would you choose to have it again for a similar problem?- Take the ADL questionnaire (see next section)- If in person (part of standard care, only collected by study staff, measurements performed by caregivers): Perform the following measurements: range of motion of the PIP joint of the affected finger (including noting any flexion contracture), distance fingertip to distal palmar crease (DPC), and grip strength using Jamar 2 setting.

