	
2. VAS3. How many oxycodone or other narcotic medications are you taking post-op4. Are you able to return to work?5. Are you satisfied with the procedure, and would you choose to have it again for a similar problem? 
- Take the ADL questionnaire (see next section)- If in person (part of standard care, only collected by study staff, measurements performed by caregivers): Perform the following measurements: range of motion of the PIP joint of the affected finger (including noting any flexion contracture), distance fingertip to distal palmar crease (DPC), and grip strength using Jamar 2 setting.-
Visit/Telephone call 7 (6 months +- 1 week after surgery)	
- Take the following questionnaire:- 1. Are you able to return to activities of daily living, and what activities do you still have trouble doing? You can list the activities you are having trouble with.2. VAS3. How many oxycodone or other narcotic medications are you taking post-op4. Are you able to return to work?5. Are you satisfied with the procedure, and would you choose to have it again for a similar problem? 
- Take the ADL questionnaire (see next section)- If in person (part of standard care, only collected by study staff, measurements performed by caregivers): Perform the following measurements: range of motion of the PIP joint of the affected finger (including noting any flexion contracture), distance fingertip to distal palmar crease (DPC), and grip strength using Jamar 2 setting.

We will call or e-mail patients to ask them to complete questionnaires (see above) through Redcap.

Procedures

The intervention groups consist of:

- Open trigger finger release
 - o The A1 pulley is reached through a transverse incision under local anesthesia and monitored anesthesia care. It is then divided longitudinally. The patient is asked to flex and extend the affected finger. If triggering has been resolved, the wound is closed with sutures (12).
- Ultrasound-guided trigger finger release
 - o The A1 pulley is identified with the use of ultrasound. The pulley is released with a trigger finger device under local anesthesia and monitored anesthesia care (9).

Specific data variables to be collected

The variables that will be collected are:

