- Range of motion of the PIP joint of the affected finger using a goniometer (in degrees), including any flexion contracture + Distance of fingertip from DPC
- Grip strength in the affected as well as contralateral hand using a dynamometer at Jamar 3 setting (in lbs)
- Return to activities of daily living. One question is: 'What activities can't you do?'. We also take a questionnaire to rate their ability to do certain activities (see questionnaire under this section). Patients can rate their ability to perform each activity on a scale from 1 to 5 (1 indicating no difficulty and 5 indicating unable to perform).
- VAS (a pain scale from 1 – 10, reported by the patient)
- How many oxycodone or other narcotic medications are you taking post-op? The number of pills taken will be given.
- Return to work. Patients give a date of when they started working again. Then we'll calculate the return to work in weeks
- Are you satisfied with the procedure, and would you choose to have it again for a similar problem? Answered with yes or no.
- Complications (i.e., trigger finger recurrence, infection, bleeding, etc.)

ADL questionnaire

Mass General Brigham Institutional Review Board
Intervention/Interaction Detailed Protocol

Opening jar	1	2	3	4	5
Driving	1	2	3	4	5
Household Chores	1	2	3	4	5
Carrying Groceries	1	2	3	4	5
Buttoning	1	2	3	4	5
Bathing	1	2	3	4	5
Cooking	1	2	3	4	5
Writing	1	2	3	4	5
Dressing	1	2	3	4	5
Shopping	1	2	3	4	5
Holding a book	1	2	3	4	5
Eating	1	2	3	4	5
Using a Computer	1	2	3	4	5
Holding a Phone	1	2	3	4	5
Using Toilet	1	2	3	4	5

Description of plans for return of research results as applicable

Not applicable

Definition of primary and secondary outcomes/endpoints

Primary endpoints:

- The 5 questions asked in the section above, together with the *ADL questionnaire*
- Recurrence of trigger finger or incomplete release

Secondary endpoints:

- Range of motion of the PIP joint of the affected finger (including noting any flexion contracture)
- Distance fingertip to distal palmar crease
- Grip strength in the affected hand
- Other complications than recurrence of trigger finger or incomplete release

Local site restrictions or site-specific procedures as applicable

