The visits during the first 3 months are part of standard care. Patients with persistent problems will be seen at the 6-month follow-up as part of standard care. If they are doing well clinically, we will only contact them by phone or email to complete these questionnaires using Redcap (see above for the scheme).

Remuneration as applicable

There is no remuneration for this study.

2. Risks and Discomforts

Trigger finger release is a standard procedure (whether it is open or ultrasound-guided) for a trigger finger.

This study's foreseeable risks and discomforts include the time required to complete the measurements and questionnaires. All electronic information (like measurements in Excel files) will be stored on

password-protected computers in a locked office that only study staff members can access. Study data of the questionnaires will be collected and maintained electronically using REDCap, a secure and HIPAA-compliant web-based application to which only study staff will have access. This limits the risk of a data and confidentiality breach, though it is a possibility.

We do not foresee additional risks for subjects participating in the study. Subjects will receive usual care, regardless of their participation. Physicians will be readily accessible for consultation should a subject experience discomfort while completing the measurements and questionnaires or at any time during the study.

3. Benefits

Patients will not receive any direct benefits from this study. However, their participation will help us to determine clinical outcomes after ultrasound-guided and open trigger finger release, which can help patients and physicians in shared decision-making. Potential benefits of ultrasound-guided trigger finger release could be a faster recovery (faster return to work) and better patient-reported aesthetics.

4. Statistical Analysis

Normally distributed continuous data will be stated as mean \pm standard deviations, non-normally distributed continuous data as medians with interquartile ranges and categorical data as frequencies and percentages.

We plan to statistically compare the postoperative clinical data of open trigger finger release to ultrasound-guided trigger finger release.

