We will use a student t-test to analyze normally distributed continuous data. When we compare data at two different time points within a group, we will use a paired student t-test. When we compare continuous data of two different groups, we will use an unpaired student t-test.

We will use a Mann-Whitney U test if the continuous data is not normally distributed.

We will use Fischer's exact test or a Chi-squared test for differences in categorical variables, depending on the number of events in the different groups.

Power analysis

We have performed a power analysis to find differences between two independent means (normally distributed) with alpha = 0.05, power = 0.80, and effect size 0.5. This would require a total sample size of 102 patients (51 in each group). If the data is non-normally distributed with the same alpha, power, and effect size, we would need a total of 106 patients (53 in each group).

This power analysis is performed for our most important primary outcomes: the 5-question and ADL questionnaires.

5. Monitoring and Quality Assurance

The full-time research coordinator and principal investigator are responsible for adherence to all IRB policies and guidelines and for the accuracy and completeness of all forms, entries, and informed consent.

Study data will be maintained in a locked filing cabinet and/or on password-protected computers. Questionnaires and self-reported responses will not become part of the subject's medical record. Hard copies of study-related data and forms will be stored in a lockable file cabinet. Only the investigators and study staff will have access to this information. Any magnetic or electronic information will be saved in password-protected computers, which only study staff members can access. REDCap, secure and HIPAA-compliant, will be used to collect all answers.

For guidance, refer to the following Partners policies:

Data and Safety Monitoring Plans and Quality Assurance

https://partnershealthcare-public.sharepoint.com/ClinicalResearch/DSMP_in_Human_Subjects_Research.pdf

Reporting Unanticipated Problems (including Adverse Events)

https://partnershealthcare-public.sharepoint.com/ClinicalResearch/Reporting_Unanticipated_Problems_including_Adverse_Events.pdf

6. Privacy and Confidentiality

- Study procedures will be conducted in a private setting
- Only data and/or specimens necessary for the conduct of the study will be collected

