Telephone Script – Clinical and Patient-Reported Outcomes After Ultrasound-guided vs Open Trigger Finger Release

"Hello, is this Mr./Mrs. X? My name is [name]. I am a researcher from the Hand and Upper Extremity Service at [Massachusetts General Hospital/Brigham and Women's Hospital]. I am following up with you about the study you are enrolled in titled, "Clinical and Patient-Reported Outcomes After Ultrasound-guided vs Open Trigger Finger Release" to see if you would be able to take our questionnaire. Would now be an OK time to speak about this?"

If no: "Is there a better time to speak in the future?"

If yes:

"I will first revise what the study is about that you are enrolled in. We are studying the clinical and patient-reported outcomes of patients who had ultrasound-guided or open surgery for a trigger finger. Basically, we would be interested in hearing about your symptoms, hand functionality, and return to work since the operation. The entire process should take less than 5 minutes of your time and would be very valuable to us as clinicians and surgeons in the care of patients like you. Would you be interested in filling out the questionnaire over the phone or through e-mail?"

Alternatively, we would be happy to mail you the forms to complete with a self-addressed stamped envelope for return."

If yes:

Proceed with details of RedCap personalized sign-on or alternatively mailing of forms.

If no:

"We thank you for your time. Please do not hesitate to call if you would be willing to help in the future."

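### Complications other than recurrence are compared between arms, but no postoperative contact asks about them and a different team charts each arm, so ascertainment is unstandardised and can differ by arm

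*Combined protocol and SAP*

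**What the plan says.** The endpoint list in section 6 (Definition of primary and secondary outcomes/endpoints) includes, as secondary, "Other complications than recurrence of trigger finger or incomplete release". The list of variables to be collected has the entry "Complications (i.e., trigger finger recurrence, infection, bleeding, etc", with no question, source, assessor, definition or time window. Most other entries in that list have a method: goniometer, dynamometer, pill count, a return-to-work date, a yes/no answer.

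The Study visits table gives six postoperative contacts (2–4, 6–8, 13–15 and 27–29 days, 3 months, 6 months). Each has the same five questions (daily activities, pain, narcotic use, work, satisfaction) and the ADL form. Range of motion, fingertip distance and grip are added under the condition "If in person (part of standard care, only collected by study staff, measurements performed by caregivers". Each contact is labelled as a visit or a telephone call.

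Under Local site restrictions, visits in the first 3 months are described as standard care. At 6 months, only patients with persistent problems are seen; the others are contacted by phone or e-mail. Section 3 limits the stated chart review to patient characteristics and disease-related variables.

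On allocation, section 5 says: "Depending on the treating surgeon, patients will either be treated with an open trigger finger release or an ultrasound-guided trigger finger release". Section 3 adds that one surgeon does every ultrasound-guided release and all other surgeons operate open.

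The Statistical Analysis section says: "We plan to statistically compare the postoperative clinical data of open trigger finger release to ultrasound-guided trigger finger release". For categorical data: "We will use Fischer's exact test or a Chi-squared test for differences in categorical variables".

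**The concern.** A harm that nobody asks about is recorded only if the patient volunteers it, or if a clinician sees it and writes it down and study staff then look for it. The plan standardises none of these routes. The clinicians who would see and write down the harm also differ systematically between arms, because surgeon and procedure are the same variable here. A difference in complication rates could then reflect how thoroughly each team observes and charts, and a real difference could be hidden in the same way. A Fisher or chi-squared test on the recorded counts cannot separate the two.

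This matters because the Benefits section says the results should help patients and physicians in shared decision-making, and the complication rate of a newer technique is a figure they will look for. Harms not asked about at the time may not be recoverable later.

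**Working it through.** **Step 1: is there a planned route for the data?**

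| Possible route | What the plan provides |
|---|---|
| Questionnaire | Five questions and 15 ADL items; no complication item at any of six contacts |
| In-person visit | Range of motion, fingertip distance and grip, if in person; no complication item |
| Chart review | Patient characteristics and disease-related variables; complications not named |
| Telephone script | A general interest in "we would be interested in hearing about your symptoms, hand functionality, and return to work since the operation" |

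The script invites the patient to take the questionnaire and is not itself the instrument, so its silence adds little. The first three rows carry the point.

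**Step 2: can the route differ by arm?** Yes, because treating team and arm coincide (sections 3 and 5). Whether it does differ is not stated.

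**Step 3: how large could the effect be?** The documents give no complication rate, in-person share or detection probability. The only figure taken from the plan is 51 per arm, which was set for the questionnaires. (It reproduces as a one-sided 0.05 t-test with effect size 0.5 and power 0.80: 50.15, rounded up to 51. The plan does not state the sidedness, which is a separate matter.) Everything else below is assumed.

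Let s be the share of patients seen in person in the relevant period and c the share of events recorded without an in-person contact. Assume every event is found if the patient is seen. Then

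detection = s + (1 − s) × c, and with equal true risk the apparent risk ratio is the ratio of the two detections.

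Arm A has s = 0.95, so its detection is 0.95 + 0.05 × 0.25 = 0.963 or 0.95 + 0.05 × 0.50 = 0.975.

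| Arm B: s | Detection B (c = 0.25 / 0.50) | Apparent risk ratio B/A | Inverse A/B |
|---|---|---|---|
| 0.85 | 0.888 / 0.925 | 0.92 / 0.95 | 1.08 / 1.05 |
| 0.70 | 0.775 / 0.850 | 0.81 / 0.87 | 1.24 / 1.15 |
| 0.50 | 0.625 / 0.750 | 0.65 / 0.77 | 1.54 / 1.30 |

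The arms are left unlabelled because the documents do not say which, if either, would be seen less. The inverse column is also the true B/A risk ratio that would look like no difference. If s and c are equal in the two arms, the ratio is 1.

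In events, at an assumed 10% true risk: 51 × 0.10 = 5.1 true events per arm. Arm A records about 4.9–5.0. Arm B at s = 0.50 records 3.2–3.8, so the gap is about 1.1–1.7 events. At s = 0.85 it is under 0.4.

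**Step 4: a simpler version.** Because visits list no complication item, recording can differ even among patients who are seen. With assumed overall detection of 0.9 against 0.7, 0.5 or 0.3 and equal true risk, the apparent risk ratio is 0.78, 0.56 or 0.33. A true 5% against 10%, detected at 0.9 and 0.45, is recorded as 4.5% in both arms (0.05 × 0.9 = 0.10 × 0.45).

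**Step 5: what the test would show.** By exact enumeration at 51 per arm, Fisher's test has about 7% power for a true 5% against 10% even with full detection. With equal true risk of 10% and detection 0.9 against 0.5, it is significant in about 4% of trials. The damage is mainly to the estimates and to the reading of a null result, and at low risks seldom a false significant finding.

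**The case against.** The strongest reply is that the plan already has patients in both arms seen. Visits in the first 3 months are standard care, surgeons measure motion and grip at postoperative visits as routine, and patients with persistent problems are seen at 6 months. Complications are a listed variable, chart access exists, physicians are available throughout, and an adverse-event reporting policy is linked (its content is not in the documents). Attendance of 50% or 70% in one arm fits poorly with this. The endpoint is secondary and unpowered, and sampling error exceeds the illustrated bias.

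Most of this stands as mitigation. It does not close the gap: the schedule allows every postoperative contact to be remote, visits carry no complication item, and using charts would rest on notes written by a different team in each arm.

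A reader might infer that the bias favours the ultrasound technique, since only the open procedure is described with "If triggering has been resolved, the wound is closed with sutures (12", which could prompt an early wound check. The documents do not support that. The ultrasound description is brief and silent on closure and follow-up, and no suture or wound-check visit is scheduled in either arm. The opposite is as arguable: a single surgeon may record uniformly, while many open surgeons across several hospitals record unevenly. Nor can it be said that a harm enters the data only through the chart, since a patient could mention one in the free-text item on activities.

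**Conclusion.** The point holds as a gap in ascertainment. A compared harm endpoint has no planned question, source, definition or window, and the people most likely to record it differ by arm. The comparison can therefore be biased. The documents do not show that attendance or charting differs, so direction and size are unknown. The risk ratios above follow from assumed inputs; they are not estimates of what this study will see, and with equal attendance and charting there is no arm-related bias.

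Recurrence or incomplete release, a primary endpoint, has the same gap: no contact asks about renewed triggering and no assessor is named. The change is worth making because it alters what is collected at small cost. It does not affect the sample size.

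**What to change.** - Add one fixed yes/no complication checklist, with a date for each positive answer, to the REDCap form and the telephone follow-up at all six postoperative contacts. It should be identical in both arms and cover infection, bleeding or wound problems, new numbness, recurrent triggering, and unplanned care or a further procedure on the hand.
- Have existing study staff apply one written EPIC extraction rule, through 6 months, to every patient.
- Report patient-reported and chart-found events separately as well as combined, beside the number of in-person contacts per arm. Separate reporting matters because a uniform extraction rule does not make the underlying notes uniform.

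The cost is a protocol and REDCap amendment with IRB notice, roughly a minute more per contact, and one chart look-up per patient. No extra patients, visits or staff are needed. The downsides are slightly longer questionnaires, higher recorded rates of minor events, and self-report by patients who know which procedure they had, which can itself differ by arm.

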Institutional Review Board Intervention/Interaction Detailed Protocol

Principal Investigator: [name]

Project Title: Clinical and Patient-Reported Outcomes After Ultrasound-guided vs. Open Trigger Finger Release

Version Date: 6/6/2023

For Intervention/Interaction studies, submit a Detailed Protocol that includes the following sections. If information in a particular section is not applicable, omit and include the other relevant information.

1. Background and Significance

Trigger finger is initially treated conservatively. Conservative treatment options include modification of activities, painkiller administration, splinting, and corticosteroid injections (1). Open or minimally invasive surgical treatment can be considered if conservative treatment fails. Minimally invasive surgery options consist of ultrasound-guided or blind percutaneous trigger finger release.

Many studies have reported good clinical outcomes after ultrasound-guided trigger finger release, including low rates of catching or locking recurrence rates, high QuickDASH scores and high patient satisfaction (2-4).

Postoperative clinical outcomes of open surgery have been widely compared to percutaneous surgery (5-8). However, the comparison of postoperative results between ultrasound-guided and open trigger finger release has been scarcely reported. Nikolaou et al. reported that ultrasound-guided trigger finger release resulted in a significantly sooner return to normal activities and better patient-reported cosmetic outcomes than open trigger finger release (9). Success rates and mean QuickDASH scores did not differ significantly between these groups in this cohort.

The potential benefits of ultrasound-guided trigger finger release compared to open trigger finger release have yet to be investigated. This study aims to prospectively analyze patient-reported outcomes in patients undergoing open vs. ultrasound-guided trigger finger release.

2. Specific Aims and Objectives

This study aims to prospectively analyze clinical and patient-reported outcomes in patients undergoing open vs. ultrasound-guided trigger finger release. Patients will not be randomly assigned to one of these two groups; rather, they will undergo the type of trigger finger surgery that they already agreed to with their surgeon, and we will measure the outcomes. Because of this, the study does not change the patient's standard of care; we are simply looking to collect additional data points.

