3. General Description of Study Design

Retrospective part

Patient characteristics and disease-related (trigger finger) variables will be collected retrospectively from patient charts on EPIC.

Prospective part

This will be a prospective two-arm study. Patients will either be treated with ultrasound-guided trigger finger release or open trigger finger release (conventional method). [name] is the only surgeon within the Mass General Brigham (MGB) hospitals that performs ultrasound-guided trigger finger release. All other surgeons perform open trigger finger releases.

Surgeons will measure range of motion and grip strength preoperatively and during postoperative visits, which is part of routine care. We will also administer questionnaires to see how patients are doing postoperatively. See the '6. Study Procedures' for a more elaborate description of the visits.

4. Subject Selection

Inclusion criteria:

1. ≥ 18 years of age
2. Clinical diagnosis of trigger finger
3. Patient has failed conservative treatment or elects not to undergo conservative treatment
4. Surgeon agrees that surgery is indicated
5. Subject agrees to complete follow-up questionnaires over a 6-month period

Exclusion criteria:

1. Prior surgery on the target finger
2. History of prior surgical pulley release in the target hand
3. History of prior surgical pulley release in the contralateral hand within 3 months of enrollment or with persistent symptoms that interfere with normal daily activities or work at the time of consent
4. Corticosteroid injection in the target finger or hand within 6 weeks of surgery
5. Presence of additional process in the target wrist or hand requiring additional intervention beyond pulley release (e.g., neurolysis, mass removal, tenosynovectomy)
6. Clinically significant trauma or deformity of the upper limb (shoulder to hand) on the target side
7. Clinically significant vascular disease (including Raynaud's phenomenon) of the upper limb (shoulder to hand) on the target side
8. Clinically significant neurological disorder (including complex regional pain syndrome) of the upper limb (shoulder to hand) on the target side
9. Planned surgical or interventional procedure on the contralateral wrist or hand

10. Systemic inflammatory disease (e.g., rheumatoid arthritis, lupus)
11. Amyloidosis
12. Diabetes not controlled by a stable dose of medication over the past three months
13. Pregnant or planning pregnancy in the next 6 months
14. Workers' compensation subjects

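### The treating surgeon determines the arm, yet every stated between-arm test is unadjusted and none uses the pre-operative values collected

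*Combined protocol and SAP*

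**What the plan says.** **Allocation.** Specific Aims and Objectives states that "Patients will not be randomly assigned to one of these two groups"; instead, "they will undergo the type of trigger finger surgery that they already agreed to with their surgeon". General Description of Study Design says that one named surgeon "is the only surgeon within the Mass General Brigham (MGB) hospitals that performs ultrasound-guided trigger finger release", and that all the others operate open. Subject Enrollment confirms that the arm is determined by who treats the patient.

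**Pre-operative data.** Visit 1 in Study Procedures takes the ADL questionnaire, VAS, PIP range of motion, fingertip-to-crease distance and grip strength. The design section adds: "Surgeons will measure range of motion and grip strength preoperatively and during postoperative visits, which is part of routine care". Under Subject Enrollment, anyone who has not filled in the pre-operative questionnaire by the time of surgery is dropped. Chart data are also planned: "Patient characteristics and disease-related (trigger finger) variables will be collected retrospectively from patient charts on EPIC".

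**Analysis.** The Statistical Analysis section says "We plan to statistically compare the postoperative clinical data of open trigger finger release to ultrasound-guided trigger finger release". It names the unpaired t-test, Mann-Whitney, and Fisher's exact or chi-squared test for comparing groups. The paired t-test is confined to two time points within one group. No regression, ANCOVA, matching, stratification, propensity score or between-arm change score appears.

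**The concern.** Without randomisation, nothing makes different surgeons' patients alike before surgery. The eligibility criteria narrow the case-mix but leave room for differences. One inclusion criterion reads "Patient has failed conservative treatment or elects not to undergo conservative treatment", so patients at different points in their treatment history enter together. The diabetes exclusion is only "Diabetes not controlled by a stable dose of medication over the past three months", and Subject Selection expects patients with diabetes and thyroid disease.

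A pre-operative gap can create a false difference between techniques or hide a real one. This affects ADL and VAS among the primary endpoints, and all three functional secondary endpoints. The power analysis section calls the questionnaires the most important primary outcomes, and the Benefits section expects the results to inform shared decision-making. If adjustment is left until outcomes are known, the choice of covariates could be driven by the results.

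**Working it through.** **Inputs from the plan.** Alpha 0.05, power 0.80, effect size 0.5, 51 per group (53 if non-normal).

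**Assumed, because the documents do not give them.** The pre-operative gap between arms (0.25 or 0.5 SD), the pre/post correlation rho (0.3, 0.5, 0.7) and a two-sided test.

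**1. The plan's own figure.** For an unpaired t-test the noncentrality is d × √(n/2) = 0.5 × √(51/2) = 2.525 on 100 df. One-sided power is 0.806, which reproduces 51 per group (102). Using the Mann-Whitney relative efficiency 3/π, one-sided, 53 per group (106) gives 0.803. Two-sided, the totals would be 128 and 134, and 51 per group has power 0.706. The plan does not state sidedness. Its figures match an unadjusted comparison with no covariate.

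**2. Case A: the pre-operative score is the only confounder; no true effect, no surgeon effect.** The unadjusted difference is biased by rho × gap, so the noncentrality is rho × gap × √(51/2). Example: 0.5 × 0.5 × 5.050 = 1.262, giving 24.0% rejection.

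| Gap | rho 0.1 | 0.2 | 0.3 | 0.5 | 0.7 |
|---|---|---|---|---|---|
| 0.25 SD | 5.2% | 5.7% | 6.6% | 9.6% | 14.1% |
| 0.5 SD | 5.7% | 7.9% | 11.7% | 24.0% | 41.7% |

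ANCOVA on the pre-operative score gives 4.5% to 5.1% (simulation, 20,000 runs per cell, six cells).

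**3. Case B: the whole gap would persist without any treatment effect; no surgeon effect.** The bias is the full gap unadjusted, and (1 − rho) × gap with ANCOVA. The ANCOVA standard error is √[(1 − rho²)(2/n)(1 + (n/2)gap²/(2(n − 1)))], on 99 df. Example, rho 0.5 and gap 0.5: bias 0.25, SE 0.177, noncentrality 1.41, giving 28.8%.

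| Gap | Unadjusted | ANCOVA, rho 0.3 | 0.5 | 0.7 |
|---|---|---|---|---|
| 0.25 SD | 24.0% | 14.9% | 11.1% | 8.2% |
| 0.5 SD | 70.6% | 42.8% | 28.8% | 17.5% |

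**4. Case A plus a surgeon effect.** One ultrasound surgeon against 5 to 10 open surgeons, rho 0.5 (simulation, 100,000 runs per cell). Surgeon numbers and variance shares are assumed.

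| Surgeon share of variance | Gap 0.25: unadjusted | ANCOVA | Gap 0.5: unadjusted | ANCOVA |
|---|---|---|---|---|
| 0.01 | 13% | 9–10% | 27% | 9% |
| 0.02 | 16–17% | 13–14% | 29% | 13–14% |
| 0.05 | 24–25% | 24–26% | 34–35% | 23–25% |

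**5. Power with balanced baselines, d = 0.5, two-sided, no surgeon effect.** Replacing the SE √(2/n) by √[(1 − rho²)(2/n)] raises power from 71% to 75%, 82% and 94% at rho 0.3, 0.5 and 0.7.

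**The case against.** **No gap is shown.** Both arms share one set of criteria, and nothing says that severity steers patients to a surgeon. The diabetes, thyroid and treatment-history points show variety within the sample, not a difference between arms. This stands: bias is plausible, not demonstrated. At rho 0.1 to 0.2 with a 0.25 SD gap the inflation is negligible. One rho is also a simplification for outcomes measured from day 2 to month 6.

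**The wording is generic.** The t-test sentence does not forbid change scores. But the section names postoperative data as what is compared, and no other use of pre-operative values between arms is stated.

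**ANCOVA is not the only option.** A between-arm change score is unbiased in Case B. In Case A, though, its standardised bias has size gap × √((1 − rho)/2). At a 0.25 SD gap that is 0.148, 0.125 and 0.097, giving 11.5%, 9.6% and 7.7% at rho 0.3, 0.5 and 0.7. This is worse than the unadjusted test at rho 0.3 and no better at 0.5. The documents cannot settle which case applies. ANCOVA is better than or about equal to the unadjusted test in every scenario above.

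**Much lies beyond adjustment.** Five of the seven primary components (return to ADL, narcotic count, return to work, satisfaction, recurrence or incomplete release) have no pre-operative counterpart. Surgeon and technique are fully confounded, and at a 0.25 SD gap the gain is gone once surgeons explain about 5% of the variance. All of this stands. It limits what can be concluded; it does not justify leaving out the measured baselines.

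**Conclusion.** The concern holds. Followed as written, the plan leaves measured confounding in two primary and three secondary outcomes, although the data to reduce it are already collected. This should be corrected before outcomes are seen.

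Confidence is high on the omission, and low on the size of the bias and on how much of it adjustment would remove. With 51 per group and rho 0.3 to 0.7, a nominal 5% two-sided test rejects 6.6% to 41.7% of the time in Case A, and 24% or 71% in Case B at gaps of 0.25 or 0.5 SD. ANCOVA removes the excess in Case A and only part of it in Case B. Neither analysis separates technique from surgeon.

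**What to change.** 1. **Outcomes with a pre-operative value.** In Statistical Analysis, make the between-arm analysis of ADL, VAS, range of motion, crease distance and grip strength a linear model with arm and that outcome's pre-operative value. Name the analysis visit or visits, and define how the 15 ADL ratings form a score; the plan does neither. Add a short pre-specified set of chart covariates. The documents themselves point to failed versus declined conservative treatment, diabetes and thyroid disease. Keep the planned unadjusted tests as supportive, and report pre-operative values by arm.
2. **Primary outcomes without one.** Keep the planned tests and label them unadjusted, or adjust for pre-operative ADL and VAS where event numbers allow, with the rule for that fixed in advance.
3. **Conclusion.** Word it as one surgeon's ultrasound-guided releases against other surgeons' open releases. State that adjustment covers only measured differences and cannot separate technique from surgeon.

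**Cost.** Revised wording, slightly more analysis and reliance on model assumptions, which need checking on bounded scales. No new visit or measurement is needed for the pre-operative values. Two things need confirming. The chosen chart covariates must be in the extraction, since the design section describes them only generically and the variable list does not name them. The dynamometer setting must also be reconciled, because the visit table gives Jamar 2 and the variable list Jamar 3.
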